7.3. Withdrawal from the Study and Replacement

The subjects have the right to withdraw from the study at any time for any reason, without the need to justify. Additionally, the investigator may withdraw the subject acording to clinical judjment.

A subject will be withdrawn from the study for any of the following reasons:

- Subject withdraws consent
- Lost to follow-up
- Termination of the study
- The investigator believes that for safety reasons (eg, adverse event) it is in the best interest of the subject to stop treatment
- The subject becomes pregnant
- Failure to use an acceptable method of birth control
- Significant deviation from the protocol
- Occurrence of a treatment-related SAE
- Concurrent illness and requirement of a prohibited medication
- The subject meets any of the stopping criteria listed in Section 7.2.

If a subject is lost to follow-up, every possible effort will be made by study center staff to contact the subject and determine the reason for discontinuation; this information will be recorded on the subject's CRF.

If a subject withdraws before completing the study, the reason for withdrawal will be documented on the subject's CRF and in the source document. Study drug assigned to the withdrawn subject may not be assigned to another subject.

Should the sponsor elect to replace subjects who withdraw before they complete all study procedures, the replacement subjects will be of the same gender as the subjects they are replacing. A replacement subject will be assigned a new identification number which will be equal to the identification number of the subject being replaced plus 500. Replacement subjects will be assigned to the same treatment-sequence as the subjects they are replacing. Replacement subjects will start with Treatment Period 1.

8. STATISTICAL METHODS

This statistical plan may be revised during the study to accommodate protocol amendments and to make changes to adapt to unexpected issues in study execution and data that could affect

planned analyses. These revisions will be based on blinded review of the data, and a final plan will be issued prior to database lock.

All available data will be included in data listings and tabulations. No imputation of values for missing data will be performed.

Percentages of subjects with AEs or laboratory toxicities will be based on non-missing values.

A formal statistical analysis plan for the analysis and presentation of data from this study will be prepared before database lock. Deviations from the statistical analyses outlined in this protocol will be indicated in this plan; any further modifications will be noted in the final clinical study report.

Statistical analysis will be performed by or under supervision of the sponsor.

8.1. Sample Size Determination

The planned sample size is approximately 18 subjects dosed with 64 mg roluperidone in Treatment Phase 1 such that at least 12 subjects can complete dosing with 64 mg roluperidone and 10 mg olanzapine during Treatment Phase 2. The selected sample size is sufficient to calculate the 90% confidence interval of the estimated ratio of C_{max} and AUC of roluperidone with and without coadministration of olanzapine for a true within-subject standard deviation of 0.25 or 0.40 with maximum imprecision of 20.5% or 30.8%, respectively.

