- 27. Woman with a positive pregnancy test, who is lactating, or who is planning to become pregnant during the study.
- 28. Subject who participated in another clinical study within 3 months prior to Screening, or received roluperidone previously, or has previously participated in > 3 clinical studies with experimental medication within the past 2 years.

Test Product, Dosage, and Route of Administration:

Roluperidone will be available in a tablet form at a strength of 64 mg per day.

Oral olanzapine 10 mg will be available in a tablet form as marketed formulations.

Reference Therapy, Dosage and Mode of Administration: Not applicable

Duration of Subject Participation/Duration of Study/Duration of Treatment:

• Screening: Up to 28 days prior to admission to the clinical site

• **Inpatient admission:** Day -2

• Baseline Visit: Day -1

• **Treatment Phase 1:** Day 1 to Day 7

• **Treatment Phase 2:** Day 8 to Day 19

• End-of-study visit: 14 (+ 2 days) days after the last dose

Total possible study length: Up to 63 days

EVALUATION CRITERIA

Pharmacodynamics: Safety assessments, including adverse events, clinical laboratory, ECG, vital signs, extrapyramidal symptoms (assessed by AIMS and BARS), and suicidal ideation (assessed by the C-SSRS). The incidence of adverse events and clinically significant abnormal laboratory, vital signs, and ECGs values will be recorded based upon Investigator observation, central assessments as appropriate, and subject reporting.

Pharmacokinetics: The following plasma PK parameters after roluperidone single dose, at steady state, and when administered concomitantly with olanzapine will be calculated for roluperidone and its metabolites using non-compartmental methods: C_{max} , T_{max} , AUC_{24} , and AUC_{∞} . Additional PK parameters may be included if deemed appropriate.

CGI-S.

STATISTICAL CONSIDERATIONS

Sample Size Determination: The planned sample size is approximately 18 subjects dosed with 64 mg roluperidone in Treatment Phase 1 such that at least 12 subjects can complete dosing with 64 mg roluperidone and 10 mg olanzapine during Treatment Phase 2. The selected sample size is sufficient to calculate the 90% confidence interval of the estimated ratio of C_{max} and AUC of roluperidone with and without coadministration of olanzapine for a true within-subject standard deviation of 0.25 or 0.40 with maximum imprecision of 20.5% or 30.8%, respectively.

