5. STUDY TREATMENT

5.1. Randomization and Blinding

This is an open-label, one-sequence study; therefore, randomization and blinding will not be performed. Eighteen (18) subjects will be enrolled in the study to ensure 12 subjects complete the study. Eligible subjects will be assigned a subject identification number in sequential order.

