8.4. Pharmacokinetic Analyses

The plasma pharmacokinetic parameters after roluperidone single dose, at steady state, and when administered concomitantly with olanzapine (C_{max}, T_{max}, AUC₀₋₂₄, and AUC_∞) of roluperidone and its metabolite BFB-520 will be determined from plasma concentration data using non-compartmental methods. Pharmacokinetic parameters will be summarized by arithmetic mean, SD, geometric mean, coefficient of variation (CV%, both arithmetic and

geometric), median, minimum and maximum.

Plasma concentration data will be summarized by treatment group (roluperidone alone, roluperidone + olanzapine). A nominal time point will be used for the presentation of tables and figures.

Treatment ratios (roluperidone + olanzapine versus roluperidone alone) for C_{max} , AUC_{0-24} , and AUC_{∞} , following at steady state, will be summarized using the same descriptive statistics as above. LS means (\pm 90% confidence interval [CI]) for log transformed C_{max} , $AUC_{0.24}$, and AUC_{∞} will be evaluated by a linear mixed effects model with a fixed term for treatment and a random term for subject, fit by estimated generalized least squares with restricted maximum likelihood estimates of random effects. If deemed relevant to test for a treatment difference in T_{max} , a Wilcoxon signed rank test will be used.

The plasma pharmacokinetic parameters of olanzapine from Day 17 will be compared with its pharmacokinetic profiles available in published literature.

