3. GENERAL STATISTICAL CONSIDERATIONS

3.1. SAMPLE SIZE AND POWER

The planned sample size is approximately 18 subjects dosed with 64 mg roluperidone in Treatment Phase 1 such that at least 12 subjects can complete dosing with 64 mg roluperidone and 10 mg olanzapine during Treatment Phase 2. The selected sample size is sufficient to calculate the 90% confidence interval of the estimated ratio of C_{max} and AUC of roluperidone with and without coadministration of olanzapine for a true within subject standard deviation of 0.25 or 0.40 with maximum imprecision of 20.5% or 30.8%, respectively.

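### The 'maximum imprecision' of 20.5% and 30.8% describes only the shorter, lower side of the 90% CI for the roluperidone ratio; the matching upper side is about 25.8% and 44.4%

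*Protocol*

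**What the plan says.** Protocol 8.1 plans for about 18 subjects dosed in Treatment Phase 1, "such that at least 12 subjects can complete dosing with 64 mg roluperidone and 10 mg olanzapine during Treatment Phase 2". It continues: "The selected sample size is sufficient to calculate the 90% confidence interval of the estimated ratio of C_{max} and AUC of roluperidone", comparing co-administration with roluperidone alone, "for a true within-subject standard deviation of 0.25 or 0.40 with maximum imprecision of 20.5% or 30.8%, respectively". The synopsis repeats this, and SAP 3.1 has the same figures: "standard deviation of 0.25 or 0.40 with maximum imprecision of 20.5% or 30.8%, respectively".

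None of the three places says which side of the interval the percentage describes, what it is a percentage of, which formula was used, or with what probability the maximum holds.

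The planned analysis in Protocol 8.4 and SAP 5.2.4 is "a linear mixed effects model with a fixed term for treatment and a random term for subject", applied to log-transformed Cmax, AUC0-24 and AUC∞ with 90% CIs.

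**The concern.** A confidence interval that is symmetric in logs becomes asymmetric when back-transformed to a ratio. If the log half-width is h, the limits are exp(−h) and exp(h) times the estimate, and the distance above, exp(h) − 1, always exceeds the distance below, 1 − exp(−h). A single percentage called the maximum should therefore be the upper one.

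This sentence is the only precision argument for at least 12 completers. The PK objective has to be able to describe a rise in roluperidone exposure under olanzapine as well as a fall, and for a rise the upper distance is the relevant one. A reader who takes 30.8% at face value would expect an estimated ratio of 1.00 to have an upper limit no higher than about 1.31.

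**Working it through.** **Inputs.** From Protocol 8.1: n = 12 completers, 90% two-sided CI, within-subject SD 0.25 or 0.40 (taken as log scale), stated figures 20.5% and 30.8%. From Protocol 5.1 and 8.4: one sequence, each subject its own control, log scale, so the comparison is paired with 11 degrees of freedom.

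**Step 1. Which side do the stated figures describe?** For a fixed n, h is proportional to the SD, so the two log half-widths must stand in the ratio 0.40/0.25 = 1.60. Allowing for rounding (20.45–20.55% and 30.75–30.85%):

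| Reading of the percentage p | Log half-width | Ratio of the two | Fits 1.60? |
|---|---|---|---|
| Lower side | −ln(1 − p) | 1.597 to 1.612 | yes |
| Upper side | ln(1 + p) | 1.435 to 1.445 | no |
| Symmetric ± | p | 1.496 to 1.509 | no |

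This step assumes nothing about assurance level, or about t versus z. Reading 0.25 and 0.40 as coefficients of variation does not help: the lower-side half-width per unit of log SD is then 0.932 and 0.956, which disagree, as do the upper-side values, 0.757 and 0.697.

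**Step 2. Upper side implied by the stated figures alone.**
- SD 0.25: 1/(1 − 0.205) − 1 = 25.8%
- SD 0.40: 1/(1 − 0.308) − 1 = 44.5%

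**Step 3. Reproducing the plan's figures.** The plain t interval evaluated at the assumed SD is h = t(0.95, 11) × √(2/12) × SD = 0.7332 × SD, which gives 0.1833 and 0.2933. Its sides are 16.7% and 25.4% below, 20.1% and 34.1% above; neither pair matches. Adding a 90% assurance factor for the estimated SD:

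h = t(0.95, 11) × √(2/12) × SD × √(χ²(0.90, 11)/11) = 0.9188 × SD

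| SD | h | Lower, 1 − exp(−h) | Stated | Upper, exp(h) − 1 |
|---|---|---|---|---|
| 0.25 | 0.2297 | 20.52% | 20.5% | 25.82% |
| 0.40 | 0.3675 | 30.75% | 30.8% | 44.41% |

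Both stated figures are reproduced as lower-side distances. As multiples of the estimate, the interval is 0.795 to 1.258 (SD 0.25) and 0.692 to 1.444 (SD 0.40).

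A grid over n from 5 to 30, 90% or 95% confidence, no assurance or 50–99%, and the SD as within-subject or of the difference found six settings matching both figures. All were lower-side. Only the one above has n = 12 with a 90% CI.

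**Step 4. How often the upper side exceeds the stated maximum.** If the assumed SDs are true,

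P = P(χ²(df) > df × [ln(1 + p)/(t × √(2/n) × SD)]²), with df = n − 1.

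- n = 12: 0.41 (SD 0.25) and 0.60 (SD 0.40)
- n = 18: 0.04 and 0.16

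For comparison, at n = 12 the lower side exceeds the stated figures in about 10% of trials, as a 90% assurance bound implies.

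**The case against.** Nothing is miscalculated: on a reasonable basis the figures reproduce, and this stands. The fault is in what they are said to describe.

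The term imprecision is also undefined, and 1 − exp(−h) equals the gap from the estimate to the upper limit divided by the upper limit. On that definition 20.5% and 30.8% cover both sides, and the ratio test in Step 1 cannot rule it out. But neither document uses that denominator, distances are ordinarily read relative to the estimate, and the interval still reaches 25.8% and 44.5% above the estimate.

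A third argument is that maximum may refer only to the assurance bound on a random half-width, not to the wider side. That is probably how the word arose, but the text does not say so, and a bound that applies to one side should name it.

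On size, 25.8% and 44.4% are 90th-percentile values. At SD 0.25 the median upper side with 12 completers is 19.4%, inside the stated figure; at SD 0.40 it is 32.9%, beyond 30.8%. If all 18 complete, exceedance is uncommon at SD 0.25. These qualifications are fair, but the plan commits only to 12 completers, and with 18 and 90% assurance the lower sides would be 16.1% and 24.4%, which are not the stated figures.

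The consequence is small, and this also stands. PK is the secondary objective in the SAP, no no-effect boundary is attached to the interval, safety monitoring does not use it, and the actual limits will be reported.

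**Conclusion.** The concern holds. Relative to the estimate, the stated maximum covers only the shorter side of the interval, and the longer side is understated by 25.8 − 20.5 = 5.3 percentage points at SD 0.25 and 44.4 − 30.8 = 13.6 points at SD 0.40. For an estimated ratio of 1.00 at SD 0.40, the upper limit on the basis that reproduces the plan's figures is about 1.44, or 1.34 without the assurance factor, against the 1.31 the text suggests.

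The result rests on the log-scale analysis, which the documents state, and on reading the SDs as log-scale within-subject values, which the figures support. The 90% assurance level is an inference the sponsor must confirm; the 25.8% and 44.5% obtained by inverting the stated figures do not need it. This should be corrected because it misstates the only precision basis for the sample size, but it does not undermine the design.

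**What to change.** Replace the sentence in Protocol 8.1, the synopsis and SAP 3.1 with one that gives both limits, for example:

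> With 12 completers, the 90% CI for the roluperidone Cmax and AUC ratio is expected to extend no further than about 0.79 to 1.26 times the estimate (within-subject SD 0.25 on the log scale) or 0.69 to 1.45 times the estimate (SD 0.40), with [assurance level] probability.

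The limits are rounded outward. The sponsor should fill in the assurance level from the original calculation; 90% reproduces the figures at n = 12. The formula should be given in the SAP so that the statement can be checked.

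The cost is wording in three places and a less favourable stated precision. No additional subjects are needed and the analysis does not change.

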8.2. General Methodology

A detailed description of subject accountability including count of subjects included, exposed, completed (ie, subjects who complete the study treatment period) and discontinued along with the main reason for discontinuation, will be generated for all subjects.

All subjects who are exposed to study treatment, regardless of the amount of treatment administered, will be included in the safety population.

All subjects with no major deviations related to study drug intake (eg, vomiting), for whom the primary pharmacokinetic data are considered sufficient and interpretable, will be included in the pharmacokinetic population.

Demographic characteristics will be listed and summarized using descriptive statistics.

CGI-S

8.3. Initial Subject Characteristics

For all subjects who received at least one dose of roluperidone, descriptive statistics (mean, standard deviation, median, minimum, and maximum) will be performed for age, BMI, weight, and height. Sex and race will be listed and tabulated.

8.4. Pharmacokinetic Analyses

The plasma pharmacokinetic parameters after roluperidone single dose, at steady state, and when administered concomitantly with olanzapine (C_{max}, T_{max}, AUC₀₋₂₄, and AUC_∞) of roluperidone and its metabolite BFB-520 will be determined from plasma concentration data using non-compartmental methods. Pharmacokinetic parameters will be summarized by arithmetic mean, SD, geometric mean, coefficient of variation (CV%, both arithmetic and

geometric), median, minimum and maximum.

Plasma concentration data will be summarized by treatment group (roluperidone alone, roluperidone + olanzapine). A nominal time point will be used for the presentation of tables and figures.

Treatment ratios (roluperidone + olanzapine versus roluperidone alone) for C_{max} , AUC_{0-24} , and AUC_{∞} , following at steady state, will be summarized using the same descriptive statistics as above. LS means (\pm 90% confidence interval [CI]) for log transformed C_{max} , $AUC_{0.24}$, and AUC_{∞} will be evaluated by a linear mixed effects model with a fixed term for treatment and a random term for subject, fit by estimated generalized least squares with restricted maximum likelihood estimates of random effects. If deemed relevant to test for a treatment difference in T_{max} , a Wilcoxon signed rank test will be used.

The plasma pharmacokinetic parameters of olanzapine from Day 17 will be compared with its pharmacokinetic profiles available in published literature.

8.5. Safety Analyses

Safety will be evaluated by an analysis of adverse events, vital signs, ECG, physical examination results, and clinical laboratory tests (including blood and urine analyses), AIMS, BARS, and C-SSRS, at specified time-points during the study as outlined in the TIME AND EVENTS SCHEDULE.

Standard descriptive statistics for all safety variables will be tabulated for each treatment group and measuring time, as appropriate.

Laboratory data (hematology, clinical chemistry, and urine analysis) will be compared to the normal ranges given by the laboratory. Vital signs and ECG data will be compared to normal ranges as well as predefined change ranges. Frequencies of potentially clinically significant abnormalities will be tabulated.

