- Women of non-childbearing potential and post-menopausal as defined by spontaneous amenorrhea for at least 6 months but less than 1 year will provide a blood sample for FSH testing as screening.
- Serology (HBsAg, HBcAg, hepatitis C antibody, and HIV antibodies 1 and 2) at Screening.
- Tuberculosis testing will occur at Screening.
- Urine drug screen and alcohol breath test: potential subjects will be tested for drugs of abuse (cocaine, methadone, amphetamines, cannabinoids, opiates, benzodiazepines, barbiturates, tricyclic antidepressants) and alcohol according to the TIME AND EVENTS SCHEDULE. If the results of the urine drug screen or the alcohol breath test are positive at Screening or Baseline, the subject will not be enrolled.

Vital Signs

Vital signs will include supine blood pressure, pulse, oral/tympanic temperature, and respiratory rate.

Standing and supine blood pressure and pulse will be taken after the subject has been resting quietly for 5 minutes. Blood pressure and pulse should be taken in the arm with the highest pressure, using the same arm for each reading and for all visits. An appropriately sized arm cuff will be used, and the size of the cuff should remain constant for all visits. After blood pressure has been assessed in the supine position, blood pressure will be re-measured within 3 minutes of standing).

Electrocardiogram

ECG will be recorded in triplicate (1 minute apart within 5 minutes). During the collection of ECG data, subjects should be in a quiet setting without distractions (eg, television, cell phones). Subjects should rest in a supine position for at least 10 minutes before ECG collection and should refrain from talking or moving arms or legs. If blood sampling or vital sign measurement is scheduled for the same time point as ECG recording, the ECG should be performed first, followed by vital sign measurements, and blood draws.

Three 12-lead ECGs will be recorded at a paper speed of 25 mm per second until 4 regular consecutive complexes are available. Computer-generated interpretations of ECGs should be reviewed for data integrity, reasonableness and online safety assessment.

ECGs will be overread by an ECG central reader. The following ECG intervals will be measured: RR, PR, QRS, and QT. Electrocardiogram monitoring will include the evaluation of lengthening of QTcF. A qualitative assessment of the T-wave morphology will be made by the central reader.

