12. ETHICAL ASPECTS

12.1. Study-Specific Design Considerations

This study is being conducted to evaluate the pharmacokinetics, pharmacodynamics, safety, and tolerability of roluperidone and olanzapine.

This study will be performed in subjects with schizophrenia who will receive no benefit from participation in the study. Subjects will be exposed to an investigational drug that may have adverse effects, such as headache, nausea, postural hypotension and somnolence. In addition they will be exposed to a marketed drug olanzapine which may induce well known adverse effects such as EPS, sedation, constipation, blurry vision, weight gain. In this and all clinical pharmacokinetic studies, there are risks associated with the collection of multiple blood samples.

Potential subjects will be fully informed of the risks and requirements of the study and, during the study, subjects will be given any new information that may affect their decision to continue participation. They will be told that their consent to participate in the study may be withdrawn at any time with no reason given and without penalty or loss of benefits to which they would otherwise be entitled. Only subjects who are fully able to understand the risks, benefits, and potential adverse events of the study, and provide their consent voluntarily will be enrolled. No undue incentives will be provided.

Safety of Dose

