^b Vital signs include blood pressure (standing and supine), pulse, oral/tympanic temperature, and respiratory rate. During Treatment Phase 1, vital signs are assessed prior to PK sampling at pre-dose and 6 hours post-dose on Days 1-7. During Treatment Phase 2, vital signs are assessed prior to PK sampling at pre-dose and 6 hours post-dose on Days 8-17 and 24 hours after last dose of study drug is administered (eg, Days 18 and 19).

^c Three sets of triplicate ECGs (1 minute apart within 5 minutes; total of 9 ECGs are recorded at Baseline (Day -1). Other ECG assessments are recorded in triplicate prior to PK sampling. During Treatment Phase 1, ECGs are recorded at pre-dose and 6 hours post-dose on Days 1-7. During Treatment Phase 2, ECGs are recorded pre-dose and 6 hours post-dose on Days 8-17 and 24 hours and 48 hours after last dose of study drug is administered (eg, Days 18 and 19).

^d CYP2D6 genotyping to be performed.

e Urinalysis will be performed by dipstick. Urine will be sent to the laboratory for microscopic analysis only in the event that the dipstick results are abnormal.

f After vital signs and triplicate ECG. During Treatment Phase 1, PK samples for roluperidone will be obtained at time 0 (pre-dose), 1, 2, 3, 4, 5, 6, 8, 10, 12, 14, 16, 18, and 24 hours post-dose on Days 1 and 7, at 6 hours post dose on Day 2, and at pre-dose and 6 hours post-dose on Days 3-6. During Treatment Phase 2, PK samples for roluperidone and olanzapine will be obtained at 6 hours post-dose on Day 8, time 0 (pre-dose) and 6 hours post-dose on Days 9-16, and starting on Day 17 at time 0 (pre-dose), 1, 2, 3, 4, 5, 6, 8, 10, 12, 14, 16, 18, 24, 28, 32, 36, and 48 hours post-dose. If a significant prolongation in QT is observed, a PK sample should be obtained.

MIN-101C18

Statistical Analysis Plan Final Version

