5.3.4. Other Safety Analyses

Descriptive summaries of vital signs and their respective change from Baseline values will be presented by time point and treatment group. The number and percentage of subjects with PCS vital signs occurring post-baseline will also be summarized by time point and treatment group. All abnormalities that occur post-baseline, regardless of Baseline status will be included. All vital signs will be listed with PCS vital signs flagged.

Table 3. Criteria For Potentially Clinically Significant Vital Signs

Vital Sign Parameter	Flag	Criteria
Systolic Blood Pressure	High	≥ 150 mmHg
(mmHg)	Low	≤ 80 mmHg
Diastolic Blood Pressure	High	≥100 mmHg
(mmHg)	Low	≤ 45 mmHg
Heart Rate (bpm)	High	> 115 bpm
	Low	< 45 bpm
Temperature (°C)	High	≥ 38 °C
	Low	< 35 °C

ECG parameters and their change from Baseline (using both Study Baseline and Treatment Phase 2 Baseline) will be summarized with descriptive statistics by time point and treatment group. ECG parameters will include heart rate, PR interval, RR interval, QRS interval, QT interval, and QTc interval corrected for heart rate using QTcB and QTcF. QTcF values will also be tabulated for their absolute values and tabulated relative to Baseline measurements in order to detect individual QTcF changes.

Additionally, the number and percentage of subjects with post-baseline QTcF interval > 450 - 480 milliseconds (msec), > 480 - 500 msec, or > 500 msec will be summarized, as will the number and percentage of subjects with QTcF interval increases from Baseline of > 30 - 60 msec or > 60 msec. For these summaries, worst-case assignments will be made to ensure subjects with such values are not counted more than once. For example, a subject with QTc interval > 500 msec will count once in the > 500 msec category and will not appear in the > 450 - 480 or > 480 - 500 msec categories. Similar conventions will be used for the > 30 - 60 and > 60 msec categories.

All ECG assessments and abnormalities in ECG waveform that are changes from Baseline readings will also be reported in a listing.

Final Version

Table 4. Potentially Clinically Significant Criteria for ECG

[figure not shown]
Variable	Units	PCS Criteria Low Values	PCS Criteria High Values	Change from Baseline or Observed Value
Heart Rate	beats/min	<45	>115	-
QTcF Interval	msec	-	>450 Males >470 Females	>30-60, > 60, > 450-480, > 480-500, > 500
QRS Interval	msec	-	>120	-
PR Interval	msec	-	>220	-

All physical examination results will be listed.

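### The SAP sets no change ranges for vital signs although Protocol 8.5 promises them, and it plans no within-subject standing-minus-supine blood pressure summary

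*Protocol*

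**What the plan says.** **Protocol, analysis.** Section 8.5, repeated in the synopsis, says: "Vital signs and ECG data will be compared to normal ranges as well as predefined change ranges". It gives no numerical ranges for either type of data. Section 8 adds: "Deviations from the statistical analyses outlined in this protocol will be indicated in this plan", meaning the SAP.

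**Protocol, measurement.** Section 6.5 describes the procedure: "After blood pressure has been assessed in the supine position, blood pressure will be re-measured within 3 minutes of standing". Footnote b of the Time and Events Schedule lists both positions and sets the times: pre-dose and 6 hours post-dose on Days 1-17, then 24 and 48 hours after the last dose.

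**Protocol, risk.** Section 12.1 lists the investigational drug's possible adverse effects, "such as headache, nausea, postural hypotension and somnolence". Section 1.2 describes roluperidone as an antagonist at alpha-1A and, to a lesser extent, alpha-1B receptors. Stopping criterion 11 in Section 7.2 gives documented orthostatic hypotension as an example of a known cause of syncope or severe dizziness.

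**SAP.** Section 5.3.4 plans descriptive summaries of vital signs and of their change from Baseline, and then: "The number and percentage of subjects with PCS vital signs occurring post-baseline will also be summarized by time point and treatment group". Table 3 gives the criteria: systolic at or above 150 or at or below 80 mmHg; diastolic at or above 100 or at or below 45 mmHg; and absolute limits for heart rate and temperature. For ECG, the same section defines QTcF increases of >30-60 and >60 msec. Position appears only in schedule footnote b of Section 1.2: "Vital signs include blood pressure (standing and supine), pulse, oral/tympanic temperature, and respiratory rate". Section 7 anticipates no deviations.

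**The concern.** One protocol sentence covers vital signs and ECG together, and the SAP carries out the change-range part for ECG only. A programmer following the SAP would produce no categorical table of vital-sign change, and no reader of the SAP would learn that a planned comparison had gone.

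The second gap is postural. The trial has each subject's pressure taken lying and then standing, and it names postural hypotension as an effect of the study drug. Yet the SAP derives no difference between the two readings and does not say which of them Table 3 judges. Safety and tolerability of coadministration is the SAP's primary objective, with blood pressure among its listed measures. As written, that objective receives group means and isolated extreme values, but no count of subjects whose pressure fell on standing or from Baseline.

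**Working it through.** There is no planned figure to reproduce. The check is a comparison of text, followed by arithmetic on the Table 3 limits.

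**1. Commitment against plan**

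| Item | Protocol 8.5 | SAP 5.3.4 |
|---|---|---|
| ECG, normal range | promised | Table 4 limits |
| ECG, change range | promised | QTcF >30-60 and >60 msec |
| Vital signs, normal range | promised | Table 3 limits |
| Vital signs, change range | promised | none defined |
| Vital signs, descriptive change from Baseline | covered by descriptive statistics | planned |
| Standing minus supine | not promised | not planned |

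The table and listing index in SAP Section 9 has vital signs by time point, potentially clinically significant vital signs, and two listings. It has no change-category table and no postural table.

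**2. Number of paired readings**

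Inputs are from schedule footnote b of the protocol.

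- Treatment Phase 1: 7 days × 2 = 14
- Treatment Phase 2: 10 days × 2 = 20
- Days 18 and 19: 2
- Total: 14 + 20 + 2 = 36 pairs per completer

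Screening, Baseline and EOS readings are not counted. The SAP's version of the footnote mentions only 24 hours after the last dose but still names Days 18 and 19, hence about 36.

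**3. Largest fall that Table 3 leaves unflagged**

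Assume pressure is recorded in whole mmHg. The largest unflagged fall is the highest unflagged value minus the lowest unflagged value.

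- Systolic: flagged at ≥150 and ≤80, so 81 to 149 is unflagged; 149 − 81 = 68 mmHg.
- Diastolic: flagged at ≥100 and ≤45, so 46 to 99 is unflagged; 99 − 46 = 53 mmHg.

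This applies equally to a fall from Baseline and a fall on standing. For example, a systolic change from 130 supine to 100 standing, 30 mmHg, raises no flag. These are limits on what can pass unflagged. They do not show how often it would happen.

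**4. Whether the planned descriptive summaries fill the gap**

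If both positions are summarised separately and all pairs are complete, mean(standing − supine) = mean(standing) − mean(supine), so the average postural change can be recovered. The spread cannot: Var(standing − supine) = Var(standing) + Var(supine) − 2 Cov(standing, supine), and the covariance is not reported. Nor can the number of subjects with a large fall. As an illustration with 18 subjects, a mean fall of 5 mmHg arises if every subject falls by 5, and also if 3 fall by 30 and 15 do not change, since 3 × 30 / 18 = 5.

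**5. Whether both positions are certain to reach the summary**

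SAP 3.2.4 keeps one result per nominal time point when an assessment is collected more than once, taking the one closest to schedule and, in a tie, the earlier. Supine and standing pressure share a nominal time point, and the SAP nowhere calls them separate parameters. The sponsor probably means to keep both, but the text does not say so.

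**The case against.** The strongest reply has five parts.

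- **No criteria were removed.** A reader might infer that the SAP deleted a set of vital-sign change limits. The protocol lists none, so this reply stands: what is absent is the promised comparison.
- **The data are used.** A reader might infer that the paired readings go unused. They do not: vital signs and change from Baseline are summarised and listed, the footnote includes both positions, and a standing systolic of 80 mmHg or lower could be flagged. This stands, but it leaves the paired difference and the count of subjects unplanned.
- **The protocol promises no postural analysis.** Change ranges most naturally mean change from Baseline. This stands. The standing-minus-supine summary is a recommended improvement, not a missed commitment.
- **SAP Section 7 does not certify agreement with the protocol.** Its second sentence concerns deviations from the SAP itself, so it is weak evidence of a false statement. Even so, the omission is recorded nowhere in the SAP, and Protocol Section 8 says it should be.
- **Clinical detection exists elsewhere.** Symptomatic falls can be reported as adverse events, syncope is an event of special interest, and unexplained syncope or severe dizziness is a stopping criterion. This limits the consequence but does not supply the count, and asymptomatic falls may not be reported.

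**Conclusion.** The point holds as a gap in the SAP with a cheap remedy. Protocol 8.5 promises a comparison of vital signs with predefined change ranges. The SAP defines none, does not record the departure, and does not say which position Table 3 judges. Separately, about 36 supine and standing pairs per completer have no planned within-subject summary, although postural hypotension is a named effect of roluperidone. Assuming whole-mmHg recording, falls of up to 68 mmHg systolic and 53 mmHg diastolic can pass Table 3 without a flag.

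Two stronger readings are tempting. One is that the combination carries an additive hypotensive risk. The documents attribute alpha-1 antagonism and postural hypotension to roluperidone only; for olanzapine they list other receptor affinities and effects, and no hypotension. The other is that absolute limits miss most postural falls. Nothing in the documents gives a frequency, so only the size of fall that could go unflagged can be stated.

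**What to change.** Amend SAP 5.3.4 and Table 3 as follows.

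1. State that supine and standing blood pressure are separate parameters, exempt from the one-result-per-time-point rule in SAP 3.2.4 with respect to each other, and apply the Table 3 limits to each.
2. Add change-from-Baseline categories for vital signs, with thresholds set by the sponsor, and name the Baseline used. This meets Protocol 8.5. If the sponsor prefers not to, record the departure in the SAP as Protocol Section 8 requires.
3. Derive standing minus supine systolic and diastolic pressure at each time point. Summarise it by time point and treatment group, with the number of subjects exceeding a sponsor-specified fall. Include pulse only if standing pulse is recorded: the sentence on re-measurement in Protocol 6.5, "blood pressure will be re-measured within 3 minutes of standing", mentions pressure alone, while an earlier sentence there can be read as covering both.

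The cost is SAP wording and one additional descriptive table. No new data, visits or changes to subject management are needed. The drawback is a further set of unadjusted counts in about 18 subjects, which should be read descriptively.
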